- g. Exposure to SLE SOC will be assessed in the exposed and comparator groups at LMP2 with a look-back period of 5-half-lives of relevant drug. Exposure to anifrolumab will be assessed from LMP2 until end of the first trimester of pregnancy for MCM outcome and anytime during the pregnancy for mCM outcome with a maximum look-back period of 16-weeks (time for anifrolumab concentration to fall below the LLOQ for 95% of patients) prior to LMP2
- h. Comorbidities and covariates measured during pregnancy may include maternal smoking, alcohol and substance abuse, gestational diabetes
- i. First of the following: diagnosis of CM, death, emigration, end of study period (reaching the age of 1 year), and administrative data cut off
- j. Covariates measured at index date may include maternal socioeconomic status (SES), age at LMP2

[figure not shown]

Figure 2: Overview of the study design, for adverse pregnancy outcomes

- a. Diagnosis of SLE before pregnancy
- b. Women with a continuous enrolment in the database for ≥ 12 months prior to conception (defined as LMP2)

- c. Singleton pregnancy, mother-offspring linkage. Mother-offspring linkage will be required for ectopic pregnancy, spontaneous abortion, elective termination, stillbirth, infections requiring hospitalisation, caesarean section
- d. Women with a history of CM or chromosomal abnormalities
- e. Pregnancy associated with in vitro fertilisation (IVF), date of conception cannot be established
- f. Comorbidities and covariates measured prior to index date may include maternal diabetes, maternal pre-pregnancy BMI, obstetric history
- g. Exposure to SLE SOC will be assessed in the exposed and comparator groups at LMP2 with a look-back period of 5-half-lives of relevant drug. Exposure to anifrolumab will be assessed from LMP2 until end of pregnancy with a maximum look-back period of 16-weeks (time for anifrolumab concentration to fall below the LLOQ for 95% of patients) prior to LMP2
- h. Comorbidities and covariates measured during pregnancy may include maternal smoking, alcohol and substance abuse, gestational diabetes

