³ Singleton pregnancies will be identified based on the coding system (e.g., ICD-10) used in the data sources (see [Table 18](#)). All pregnancies will be assumed to be singleton if there is no ICD-10 or procedural code that suggests the pregnancy is multifetal. For RHEKISS singleton pregnancy will be identified with the MedDRA code for single pregnancy. Multifetal pregnancies will be excluded because they share the same maternal exposure and it is not known how medication can be absorbed, distributed, and metabolised by each of the foetuses. Moreover, CMs as well as adverse pregnancy and birth outcomes occur more frequently in twin and triplet pregnancies than in singleton pregnancies, regardless of the exposure to the drug at study.

⁴ IVF pregnancies will be excluded due to issues related to the lack of information regarding maternal covariates in cases where a donor egg was used. Further, a higher incidence of adverse pregnancy and birth outcomes (e.g., gestational diabetes, gestational hypertension, preterm labour, low birthweight) have been reported in IVF pregnancies compared to spontaneously conceived controls ([118](#), [121](#)).

⁵ For example, a patient can be considered continuously enrolled in a specific time period if that patient had a contact with healthcare services (such as drug prescription or hospitalisation) prior to that period and if emigration or death were not notified after this contact. Criteria to define continuous enrolment in the database are country specific and will be detailed in the SAP.

⁶ The exposure period of interest for MCM outcomes is the first trimester of pregnancy and for all other outcomes, anytime during pregnancy. In order to account for potential prescriptions/dispensations/administrations that could lead to an intake during the period of interest, all prescriptions/dispensations/administrations that are recorded in the 16 weeks (time for anifrolumab concentration to fall below the LLOQ for 95% of patients) prior to LMP2 will be considered ([2](#)).

STEP 2B – unexposed to anifrolumab source population

Additional inclusion criteria to be applied after data extraction to create an *unexposed source population* (mirroring the exposed SLE source population, except for the exposure itself):

- Women with a continuous enrolment⁷ in the database for ≥ 12 months prior to LMP2
- Women diagnosed with SLE before pregnancy
- Women treated with SLE SOC during pregnancy⁸

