Additional exclusion criteria to be applied after data extraction to create an *unexposed source population* (mirroring the exposed source population, except for the exposure itself):

- Women treated with anifrolumab during pregnancy and/or during the 16-week period prior to LMP2
- Pregnancies whose date of conception cannot be established

STEP 3

Step to create *exposed to anifrolumab study population* and *unexposed to anifrolumab study population*.

STEP 3A and 3B – exposed and unexposed to anifrolumab study population

Additional inclusion criteria to be applied to the exposed and unexposed source population for creating a post-data extraction overarching *exposed and unexposed study population* with only moderate to severe SLE (mirroring the exposed study population, except for the exposure itself):

- Women with moderate to severe SLE (severity assessment is based on the SLE severity algorithm, see Figure 7)

Additional exclusion criteria to be applied to the exposed and unexposed source population for creating a post-data extraction overarching *exposed and unexposed study population* (mirroring the exposed study population, except for the exposure itself):

- Women with mild SLE (severity assessment is based on the SLE severity algorithm, see Figure 7)

⁷ For example, a patient can be considered continuously enrolled in a specific time period if that patient had a contact with healthcare services (such as drug prescription/administration or hospitalisation) prior to that period and if emigration or death were not notified after this contact. Criteria to define continuous enrolment in the database are country specific and will be detailed in the SAP.

⁸ Exposure to SLE SOC will be assessed from LMP2 until end of first trimester for the outcome of MCM, and from LMP2 until end of pregnancy for all other outcomes. A look-back period of 5-half-lives of relevant drugs will be considered.

- Women with a history of CM or chromosomal abnormalities and genetic syndromes (according to available records)⁹, before delivery
- Women prescribed a confirmed teratogenic drug prior to LMP2 until end of first trimester (for MCM outcome) or end of pregnancy (all other pregnancy outcomes), with a look back period of 5-half-lives of relevant drug, in both the exposed and unexposed groups (see [Table 20](#))

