Exposure to SLE SOC and/or co-medication (excluding biologics) will be assessed from LMP2 until end of first trimester for the outcome of MCM, and from LMP2 until end of pregnancy for all other outcomes. A look back period of 5-half-lives of relevant drugs will be considered. This is to account for prescription/dispensations/administrations prior to LMP2 that gave rise to *in utero* exposure of the offspring.

SLE SOC and/or co-medications are assumed to be continued throughout pregnancy. It is common for SLE to be more active during pregnancy with a high prevalence of flares (11, 12, 28, 63, 67). The risk of adverse outcomes among pregnant women who have SLE is related to disease severity (e.g., involvement of the kidneys) and activity during pregnancy (29, 39), thus it is expected that SLE treatment would occur even in pregnancy. A sensitivity analysis accounting for actual use of SLE SOC during pregnancy is presented in Section 9.7.5.

Exposure to anifrolumab will be assessed from LMP2 until end of the first trimester for the outcome of MCM, and from LMP2 until end of pregnancy for all other outcomes (see Section 8.1), or until censoring, regardless of duration of exposure. Considering anifrolumab window of clearance (16 weeks, see definition above), all patients who receive prescriptions/dispensations/administrations of anifrolumab in the 16 weeks prior to LMP2 or during pregnancy will be considered exposed (2).

Offspring whose mother had no anifrolumab prescription/dispensations/administration in the 16 weeks prior to LMP2 or during the first trimester for the outcome of MCM, or during pregnancy for all other outcomes, will be considered unexposed.

Although, the foetus is most at risk during the period of organogenesis (i.e., during the first trimester of pregnancy), exposures during other gestational time periods may also be associated with adverse outcomes (e.g., spontaneous abortion, stillbirth, or other pregnancy complications). The identification of critical windows of exposure *in utero* provides clues to possible mechanisms of the pregnancy loss and provides guidelines for protection of the foetus. An exploratory analysis focusing on the effect of *in utero* exposure to anifrolumab in different trimesters of pregnancy on the

¹⁰ The respective half-lives of SLE SOC and co-medications will be provided in the SAP.

occurrence of select pregnancy loss outcomes (composite of spontaneous abortion and stillbirth will be assessed:

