For the select pregnancy loss outcomes, the **index date/start of follow-up**, will be defined as the LMP2 (as defined in Section 9.1) from which the pregnancy will be followed until the outcome of interest. The **exit date/end of follow-up**¹¹ will be defined as the end of the study period, death, emigration (where available), loss to follow-up (disenrollment/de-registering), or date of first diagnosis of the outcome at study, or delivery, whichever is the earliest.

The select pregnancy loss outcomes will be defined as the presence of at least one of the following criteria:

- ICD-10 code of spontaneous abortion¹² (unintended loss of an intrauterine pregnancy) which is less than 22 weeks of gestation for the European data sources (40); less than 20 weeks for the USA data sources (64);
- ICD-10 code of stillbirth¹³ (unintended foetal death occurring at or after 22 weeks of gestation for the European data sources (78); at or after 20 weeks for the USA data sources (64).

Secondary outcomes

During the outcome ascertainment period, outcome events will be identified based on ICD-10 CM codes for the USA, ICD-10 for Denmark, Finland and France; MedDRA codes for Germany recorded in patient registries.

Minor congenital malformations

For this outcome the **index date/start of follow-up**, will be defined as the LMP2 (as defined in Section 9.1) from which the foetus/offspring will be followed up for the outcome of interest. The **exit date/end of follow-up** will be defined as the end of the study period, death, emigration (where available), loss to follow-up (disenrollment/de-registering), reaching the age of 1 year or date of first diagnosis of the outcome at study, whichever is the soonest.

¹¹ Specific outcome censoring rules will be applied. For spontaneous abortion outcome specific end of follow-up will be 22 weeks of gestation for the European data sources or 20 weeks for the USA data sources further details will be specified in the SAP.

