The rationale for this sensitivity analysis is to account for actual use of SLE SOC during pregnancy in estimating the risk and relative risk of primary study outcomes. For the main analysis, the SLE SOC is assumed to be continued throughout pregnancy. In this sensitivity analysis, an exact matching criterion will be added to the PS matching step of the cohort building. For a given anifrolumab exposed pregnancy, the set of potential matches will be restricted to pregnancies unexposed to anifrolumab and exposed to SLE SOC during the same trimester(s) as the exposed pregnancy was exposed to anifrolumab. For example, if a given exposed pregnancy is exposed to anifrolumab during the second and third trimester, potential matches will be restricted to unexposed pregnancies with SLE SOC exposure during the second and third trimester. After matching, the sensitivity analysis will be conducted as described for Objectives 1-4 (see Section 9.7.2).

Exposure to anifrolumab and risk of MCM using the MACDP classification system for congenital malformations

This study comprises both European and American data sources; therefore, the MACDP USA-based classification system, in addition to the EUROCAT, for MCM will be used.

The MACDP classification system categorises and defines congenital malformations differently from EUROCAT, and the results obtained from each classification system may differ. Since it is essential to consider the potential impact of different categorisations and definitions of congenital malformations on the results, a sensitivity analysis will be performed using the MACDP classification system. The rationale of this sensitivity analysis is to examine the robustness and

reliability of the association between exposure to anifrolumab and the risk of MCM using the MACDP classification (59).

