- Misclassification may occur in the derivation of date of conception. When based on LMP, the derivation of date of conception assumes an average cycle length of 28 days and that conception occurred mid-cycle. The LMP is also subject to accuracy of recall by the woman, regularity of her cycles, and variations in the interval between bleeding and anovulation. When based on gestational age, the degree of misclassification depends on the method and accuracy of the gestational age assessment. However, the misclassification is expected to be within a range of days for most patients.

- Immortal time bias cannot be ruled out. Immortal time is the period during which the outcome of interest cannot occur because of the study design (108). In this study, there is an immortal time because a pregnancy must “survive” until initiation of treatment to be considered as exposed. Nevertheless, it is expected that most pregnant women would have exposure to anifrolumab in the first trimester, and exposure to anifrolumab initiation in the second or third trimester is not expected to be frequent. Adding to this, most outcomes that terminate a pregnancy, such as a spontaneous abortion or an ectopic pregnancy, are expected to happen in the first trimester, thus minimising the impact of this bias.
- The probability of receiving anifrolumab may be related to the length of pregnancy, to some extent. The patients with longer pregnancies have more opportunity (i.e., time) to be prescribed anifrolumab, while the patients with shorter pregnancies have less opportunity (i.e., time) to be prescribed anifrolumab. This may cause a bias in the analysis as shorter pregnancies are more likely to be included in the study cohort unexposed to anifrolumab.
- Both maternal and paternal disease history can be important predictors of the risk of adverse pregnancy outcomes because of shared environmental and genetic risk factors. For this study, no paternal data will be available because linkage to paternal data is not possible for most data sources. Therefore, offspring whose fathers have a history of CM before pregnancy will not be excluded, and no adjustments can be made for potential confounders related to fathers.

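### Two incompatible standard-of-care windows define cohort entry, and the in-pregnancy one selects comparators on surviving the pregnancy-loss outcome

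*Protocol*

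**What the plan says.** The protocol states the SOC window for cohort entry in two ways.

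- **In-pregnancy rule.** STEP 2B of Section 9.2.2 requires "Women treated with SLE SOC during pregnancy". Its footnote 8 ends the window with the first trimester for major congenital malformations (MCM), and otherwise runs it "from LMP2 until end of pregnancy for all other outcomes. A look-back period of 5-half-lives of relevant drugs will be considered". The exposure paragraphs of the abstract, the main text of Section 9.1 and Section 9.3.1 use the same end points.
- **At-LMP2 rule.** Note g under each of Figures 1 to 4 in Section 9.1 reads: "Exposure to SLE SOC will be assessed in the exposed and comparator groups at LMP2 with a look-back period of 5-half-lives of relevant drug".

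For select pregnancy loss, Section 9.3.2 says the index date "will be defined as the LMP2 (as defined in Section 9.1) from which the pregnancy will be followed until the outcome of interest". Section 9.3.1 adds that "SLE SOC and/or co-medications are assumed to be continued throughout pregnancy". The exposed source population (STEP 2A) needs anifrolumab added to SOC, given during pregnancy or in the 16 weeks before LMP2.

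**The concern.** The two rules select different women, so the cohort cannot be coded from this text without choosing one. This is not a detail left to the SAP, because the protocol states both rules.

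The choice matters for a primary outcome. Under the in-pregnancy rule, a woman without SOC on board at LMP2 enters only when a later SOC record appears. If she miscarries first, she is in neither arm. If she does not, her time is counted from LMP2, although she could not have had the event and still be in the cohort. Eligibility then depends on surviving the outcome, and propensity scores built on baseline covariates cannot undo that.

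Section 9.9 discusses immortal time only for pregnancies that must last "until initiation of treatment to be considered as exposed". It does not mention the parallel condition on comparators. The sensitivity analysis in Section 9.7.5 on actual SOC use restricts matches to pregnancies "exposed to SLE SOC during the same trimester(s) as the exposed pregnancy was exposed to anifrolumab". That is again an in-pregnancy criterion, so it does not remove the selection.

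**Working it through.** **1. The plan's own figures.** Section 9.5.2 requires 72 exposed pregnancies at 1:2, or 61 at 1:3, for pregnancy loss. The inputs from Sections 9.5.1.1 and 9.5.1.3 are a loss risk of 20%, a true risk ratio (RR) of 1, a margin of 2.5, one-sided alpha of 2.5% and 80% power. Repeating the described simulation (fixed-effect pooling, 200,000 runs) gives 81.6% power for 72 and 79.5% for 61. The closed form n = (1 + 1/k)/p × ((1.96 + 0.84)/ln 2.5)² gives 71 and 63. The stated sizes reproduce and are not in dispute.

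**2. Effect on the comparator risk.** Two quantities are assumed, because the protocol gives neither:

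- q: the share of potential comparators with no SOC on board at LMP2.
- f: the fraction of their losses that occur before the first SOC record in pregnancy.

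Those early losses leave both numerator and denominator:

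observed risk = 0.20 × (1 − qf) / (1 − 0.20 × qf)

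| q | f | Calculation | Comparator risk | RR if true RR is 1 and exposed arm stays at 20% |
|---|---|---|---|---|
| 0 | any | 0.200/1.000 | 20.0% | 1.00 |
| 0.1 | 0.25 | 0.195/0.995 | 19.6% | 1.02 |
| 0.3 | 0.5 | 0.170/0.970 | 17.5% | 1.14 |
| 0.5 | 0.5 | 0.150/0.950 | 15.8% | 1.27 |

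**3. The last column is conditional.** Exposed women need SOC too. Take q = 0.3 and f = 0.5 in the comparator, and let the exposed share be 0, 0.15, 0.3 or 0.6 with the same f. The RR is then 1.14, 1.07, 1.00 or 0.85. The last value, for example, is (0.14/0.94)/(0.17/0.97). The ratio rises only if more comparators than exposed enter late.

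**4. Power at the projected numbers.** At 10% uptake, the sources expected in the loss meta-analysis give 163 + 162 + 11 + 145 = 481 exposed. Power = Φ[(ln 2.5 − ln RR)/SE − 1.96], with SE² = 1/(exposed events) + 1/(comparator events). At 1:2, with the exposed arm unaffected and q = f = 0.5:

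- SE = √(1/96.2 + 1/151.9) = 0.130, and power is above 99%.
- With q = 0.5 and f = 0.75, power is 97%.
- At the minimum size of 72 exposed and q = f = 0.5, power would fall from 81% to 52%, but the plan projects far more than 72.

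**The case against.** Several points on the other side stand.

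- **The SOC condition applies to both arms.** STEP 2A and Section 9.3.1 restrict the main analysis to anifrolumab added to SOC, and note g covers both groups. Exposed pregnancies may also qualify through anifrolumab started late, which lowers their observed loss risk. A reader might infer that the RR is inflated and that a false safety signal follows. The documents do not establish this. The 16-week anifrolumab look-back, against five half-lives for non-biologic SOC, makes more late entry among comparators plausible, but no figure supports it.
- **Section 9.9 names an opposite pull.** It says "shorter pregnancies are more likely to be included in the study cohort unexposed to anifrolumab". This is a different mechanism, anifrolumab opportunity time, and is not a misstatement. On the plan's assumptions, 10% × 20% = 2% of pregnancies would be exposed only after the first trimester. Assuming 80% of losses fall earlier, removing these pregnancies raises the comparator risk from 20.0% to 20.3%. That offsets the SOC effect only when qf is below about 0.02.
- **Supply at home may already count.** The exposure-period text in Section 9.3.1 adds expected supply and the clearance window to the record date. If this applies to SOC, a continuous user between refills is on board at LMP2. However, the rule is illustrated only by a figure titled for anifrolumab, and women who start SOC in pregnancy remain affected either way.
- **q may be small.** Comparators must be moderate or severe in the 12 months before LMP2 by an algorithm that uses SLE medication. The continuation assumption carries treatment forward once started. It does not cover a woman not yet treated.
- **Table 20 is not evidence here.** Its short windows, such as that for azathioprine, might suggest that continuous users qualify only at their next refill. Those windows serve the teratogen exclusion, and drugs on that list lead to exclusion under STEP 3. SOC half-lives are deferred to the SAP.

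**Conclusion.** The contradiction is certain. So is the direction of the bias in the comparator loss risk among women who qualify late under the in-pregnancy rule. Objective 3b reports that risk on its own, so it is affected whatever happens in the exposed arm. The size cannot be computed from the protocol: 20% becomes 19.6% to 15.8% over the assumed range from q = 0.1, f = 0.25 to q = f = 0.5, and is unchanged if every comparator has SOC on board at LMP2.

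For Objective 4, the net direction of the RR is not fixed. The sample sizes are not in error, and power against 2.5 is little affected at the projected numbers. The harm is to the reported risk and possibly to the RR. The point concerns the loss outcomes; for MCM the SOC window already ends with the first trimester.

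**What to change.** Reconcile the passages to one SOC eligibility rule for the pregnancy-loss outcomes, identical in both arms and fixed at or before LMP2: the SOC record date plus expected supply plus clearance window must reach LMP2. State explicitly that the exposure-period rule in Section 9.3.1 applies to SOC. Carry the wording through STEP 2A, STEP 2B, footnote 8, the abstract and Sections 9.1 and 9.3.1. If in-pregnancy qualification is kept, start follow-up when the SOC criterion is met instead of at LMP2. Add the selection to Section 9.9.

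The cost is protocol wording, cohort code and some pregnancies. Comparators should be plentiful, since 90% to 95% of pregnancies are assumed unexposed and only two or three per exposed are needed. A few exposed pregnancies whose first SOC record falls after LMP2 would also leave the main loss analysis, and these are scarcer. Both groups can be kept in a sensitivity analysis. The choice should be made before data extraction, because choosing between the two rules after outcomes are seen would be post hoc.

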8.1 Objectives

Primary objectives

1. To describe and estimate the risk of **MCM** in live and non-live offspring from
 - a. women with moderate/severe SLE, exposed to anifrolumab during the first trimester of pregnancy
 - b. comparable population of women with moderate/severe SLE, exposed to SOC and unexposed to anifrolumab during the first trimester of pregnancy
2. To estimate the relative risk of **MCM** in live and non-live offspring from women with moderate/severe SLE exposed to anifrolumab during the first trimester of pregnancy compared to women with moderate/severe SLE exposed to SOC and unexposed to anifrolumab during the first trimester of pregnancy
3. To describe and estimate the risk of **select pregnancy loss outcomes** (composite of spontaneous abortion and stillbirth) in pregnancies occurring in
 - a. women with moderate/severe SLE exposed to anifrolumab anytime during pregnancy
 - b. comparable population of women with moderate/severe SLE exposed to SOC and unexposed to anifrolumab anytime during pregnancy
4. To estimate the relative risk of **select pregnancy loss outcomes** (composite of spontaneous abortion and stillbirth) in pregnancies occurring in women with moderate/severe SLE exposed to anifrolumab anytime during pregnancy compared to women with moderate/severe SLE exposed to SOC and unexposed to anifrolumab anytime during pregnancy

Secondary objectives

5. To describe demographic and clinical characteristics of
 - a. live and non-live offspring (separately) and their mothers with moderate/severe SLE exposed to anifrolumab during the first trimester of pregnancy

- b. live and non-live offspring (separately) and their mothers with moderate/severe SLE exposed to SOC and unexposed to anifrolumab during the first trimester of pregnancy
 - c. live and non-live offspring (separately) and their mothers with moderate/severe SLE exposed to anifrolumab anytime during pregnancy
 - d. live and non-live offspring (separately) and their mothers with moderate/severe SLE exposed to SOC and unexposed to anifrolumab anytime during pregnancy
6. To describe and estimate the risk of **minor Congenital Malformations (mCM)** in live and non-live offspring from
 - a. women with moderate/severe SLE exposed to anifrolumab anytime during pregnancy
 - b. comparable population of women with moderate/severe SLE exposed to SOC and unexposed to anifrolumab anytime during pregnancy

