Objective	Main features	Input Cohort/ Population	Sub-cohort Abbreviation	Additional criteria to be applied to the input Cohort/ Population
Primary cohort MCM (MCM_exp+MCM_unexp)				

Primary objective 1 & 2;
 
Secondary objective 5a-b
 
Exploratory objective 15
	
Describe and estimate the risk and relative risk of MCM.
 
Describe cohort demographic and clinical characteristics.
 
Among live and non-live offspring
	Exposed study population	MCM_exp	
INCLUSION:
 
 • MCM: Pregnancies exposed to anifrolumab during the first trimester of pregnancy (+16 weeks prior to LMP2) • All pregnancies ending in spontaneous abortion, elective termination of pregnancy and stillbirth, regardless of linkage mother-offspring within the study period • Pregnancies with linkage mother-offspring within the study time period 
EXCLUSION:
 
 • Adopted children (where information is available)

Primary objective 1 & 2;
 
Secondary objective 5a-b
 
Exploratory objective 15
	
Describe and estimate risk and relative risk of MCM.
 
Describe cohort demographic and clinical characteristics.
 
Among live and non-live offspring
	Unexposed study population	MCM_unexp	
INCLUSION:
 
 • All pregnancies ending in spontaneous abortion, elective termination of pregnancy and stillbirth, regardless of linkage mother-offspring within the study period • Pregnancies with linkage mother-offspring within the study time period 
EXCLUSION:
 
 • Pregnancies exposed to anifrolumab during the first trimester (+16 weeks prior to LMP2) (see Section 9.3.1) • Adopted children (where available)

Objective	Main features	Input Cohort/ Population	Sub-cohort Abbreviation	Additional criteria to be applied to the input Cohort/ Population
Secondary cohort mCM (mCM_exp+mCM_unexp)				

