- **Proportion of unexposed to confirmed teratogenic SLE SOC and/or non-SLE SOC drugs of 80%.** It is estimated that 80% of the SLE pregnancies are not exposed to SLE SOC and non-SLE SOC confirmed teratogenic drugs before conception, with a time period of 5-half-lives of relevant drug (see list of confirmed teratogenic drugs and half-lives in Table 20), or during pregnancy. This estimate is based on the reported use of SLE SOC and/or non-SLE SOC drugs in SLE population (47, 48).
- **Proportion of anifrolumab exposure during the first trimester of pregnancy of 80%.** The majority of the anifrolumab exposed pregnancies are expected to be unplanned and exposed to anifrolumab only in the early stages of the pregnancy, as the current recommendations indicate that anifrolumab should only be used during pregnancy if the benefit outweighs the risk to the foetus (86). We therefore used the assumption that 80% of all anifrolumab exposed pregnancies are exposed to anifrolumab during the first trimester of pregnancy.
- **Proportion of anifrolumab exposed pregnancies in women with moderate-to-severe SLE of 5% and 10%.** Based on market forecasts, uptake of anifrolumab in the general SLE population is expected to grow from 5% within two years of market launch to 20% by 5 years after market launch. Given the uncertainty of how these forecasts apply to SLE women of child-bearing potential and to use in pregnant SLE women, we used a conservative lower bound (5%) and a more realistic midpoint value (10%) for the proportion of pregnancies in women with moderate-to-severe SLE exposed to anifrolumab.

In addition, to estimate the minimum required sample size and the expected power, the following assumptions were used:

- **Non-inferiority margin of RR of 2.5.** The RR of 2.5 was based on previously reported increase in risk of MCM for exposure to a major teratogenic drug (62).

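### The STEP 2B anifrolumab exclusion lacks the first-trimester limit that defines the MCM comparator; read literally, women first treated in the second or third trimester enter neither MCM group

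*Protocol*

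**What the plan says.** Section 9.2.2 selects the cohorts in nested steps. STEP 2A places in the exposed source population any woman given anifrolumab in pregnancy or in the 16 weeks before LMP2. STEP 2B removes from the unexposed source population "Women treated with anifrolumab during pregnancy and/or during the 16-week period prior to LMP2". STEP 3 moves nobody between the two populations.

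Table 5 then draws the MCM sub-cohorts from those separate populations. MCM_exp comes from the exposed study population and requires "MCM: Pregnancies exposed to anifrolumab during the first trimester of pregnancy (+16 weeks prior to LMP2"). MCM_unexp comes from the unexposed study population and excludes "Pregnancies exposed to anifrolumab during the first trimester (+16 weeks prior to LMP2) (see Section 9.3.1").

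The definitions elsewhere are specific to the outcome:

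- Section 9.3.1 says that offspring whose mother had none in the 16 weeks before LMP2 "or during the first trimester for the outcome of MCM, or during pregnancy for all other outcomes, will be considered unexposed". The Abstract says the same.
- Objectives 1b and 2 in Section 8.1 describe the comparator as "exposed to SOC and unexposed to anifrolumab during the first trimester of pregnancy". Objectives 3b and 4, on pregnancy loss, instead require no exposure at any time in pregnancy.

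**The concern.** The steps are nested, so a woman removed at STEP 2B cannot return at STEP 4. A second- or third-trimester starter meets the protocol's definition of unexposed for MCM, but on the literal text she reaches neither MCM group.

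Three things follow for a primary outcome:

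- The cohort does not match its objective.
- The comparator group is conditioned on staying free of anifrolumab to the end of pregnancy, while MCM_exp carries no condition on later treatment.
- Only pregnancies that continued past the first trimester can be removed this way, so early endings are slightly over-represented in MCM_unexp.

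Section 9.6 has each data source holder identify the study population from Section 9.2. Two rules inside that section could therefore produce different comparators in different sources, whose results are later pooled.

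**Working it through.** **Tracing one woman: first anifrolumab dose in the second trimester, none in the 16 weeks before LMP2**

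| Step | Rule | Result |
|---|---|---|
| STEP 2A | any treatment in pregnancy | exposed source population |
| STEP 2B | any treatment in pregnancy excluded | removed from unexposed source population |
| Table 5, MCM_exp | first trimester or prior 16 weeks | fails |
| Table 5, MCM_unexp | drawn from unexposed study population | never reached |
| Section 9.3.1, objectives 1b and 2 | first trimester (with prior 16 weeks in Section 9.3.1) | unexposed |

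**Inputs**

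- First-trimester share, Section 9.5.1.1: "80% of all anifrolumab exposed pregnancies are exposed to anifrolumab during the first trimester of pregnancy".
- Uptake of 5% or 10% and MCM risk of 7%, Section 9.5.1.1.
- Expected MCM-eligible exposed pregnancies of 353 (10%) and 175 (5%), Section 9.5.1.2.

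**Reproducing the 353**

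Per source: annual eligible pregnancies × (0.2 + 0.8 × linkage) × 0.8 × 0.10 × years of study period. The Finnish duration is assumed to be 6.5 years, since launch there is unconfirmed. For Carelon Research: 179 × (0.2 + 0.8 × 0.73) × 0.8 × 0.10 × 9.1 = 102.2. The others are DAPI 114.0, France 115.1, Denmark 8.4, Finland 6.2 and RHEKISS 6.8. The sum is 352.7, against the stated 353.

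**Pregnancies that enter neither group**

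- 10% uptake: exposed at any time = 353 / 0.8 = 441; late only = 441.25 × 0.2 = 88.
- 5% uptake: 175 / 0.8 = 219; late only = 218.75 × 0.2 = 44.

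**Share of the pool that is unexposed by the MCM definition** (assuming all never-exposed eligible pregnancies have SOC)

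- 10%: never exposed = 441.25 / 0.10 × 0.90 = 3,971; share = 88 / (3,971 + 88) = 2.2%.
- 5%: never exposed = 218.75 / 0.05 × 0.95 = 4,156; share = 44 / (4,156 + 44) = 1.0%.

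**Effect on the crude RR**

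The exposed risk is the same either way, so RR with the exclusion / RR without it = comparator risk including late starters / comparator risk excluding them. The protocol gives no MCM risk for late starters. I assume a range of 0% to 21.7%, the upper figure being the highest birth-defect prevalence quoted in Section 9.5.1.1, with 7% in all others. At 10% uptake:

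- Risk 0%: (3,971 × 0.07 + 88 × 0) / 4,059 = 6.85%; ratio 6.85 / 7 = 0.978.
- Risk 21.7%: (3,971 × 0.07 + 88 × 0.217) / 4,059 = 7.32%; ratio 7.32 / 7 = 1.046.

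The shift is therefore about -2% to +5%. At 5% uptake the same calculation gives about -1% to +2%.

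**Sample size and power**

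Simulation along the lines of Section 9.5.1.3 (40,000 replicates) gave 80.3% power at 210 exposed (1:2) and 78.6% at 183 (1:3), against the planned 80%. It gave 96.0% and 98.2% at 102 + 114 + 116 exposed, against the stated 96% and 98%. The exclusion leaves MCM_exp untouched. The pool of 3,971 far exceeds the 353 × 2 = 706 to 353 × 3 = 1,059 matched comparators needed, so these figures do not move.

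**The case against.** The strongest reply is that STEP 2 was meant to be outcome-specific throughout. Footnote 6, on the STEP 2A inclusion, gives the first trimester as the period of interest for MCM. Footnote 8, on SOC treatment in STEP 2B, makes the same distinction. STEP 2B is also described as mirroring the exposed population. On that reading late starters are not exposed for MCM at STEP 2A and are not removed at STEP 2B. The selection figure (Figure 5) is not in the text available here and might show this.

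That is good evidence of intent, but it does not amend the clause. Footnote 6 belongs to the STEP 2A inclusion, footnote 8 concerns SOC only, and the anifrolumab exclusion has no footnote of its own. It can also fairly be said that Table 5's narrower exclusion proves little by being redundant after STEP 2B, since the table repeats exclusions for the other unexposed cohorts as well.

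Section 9.9 already discloses that shorter pregnancies are more likely to fall in the unexposed cohort and that late initiation should be infrequent. The disclosure is general and does not cover this mismatch, but the second statement sits uneasily with the 20% late share used for planning, so the count of 88 may be too high.

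Two stronger readings are tempting. A reader might infer that the sponsor deliberately chose never-users as the MCM comparator. The documents do not support this, because objectives 1b and 2, the Abstract, Section 9.3.1 and Table 5 all use the first-trimester rule and separate it from the any-time rule for other outcomes. A reader might also infer a material bias or a loss of power. The figures above support neither.

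**Conclusion.** The inconsistency is real on the literal text and concerns a primary-outcome cohort. The wording of STEP 2B is wider than the MCM definition used everywhere else, and the footnotes soften the conflict without removing it. Its practical size is small: about 88 pregnancies (2% of the comparator pool) at 10% uptake or 44 (1%) at 5%, with no change in required sample size or expected power. These counts rest on the 80% first-trimester planning assumption and are probably towards the high end. The crude RR range depends on the assumed risks for late starters and says nothing about direction. This is a minor wording correction, worth making because it costs almost nothing and removes a selection on later treatment.

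**What to change.** Make the STEP 2B anifrolumab exclusion outcome-specific, and change the STEP 2A inclusion to match. For MCM it should cover anifrolumab from 16 weeks before LMP2 to the end of the first trimester; for all other outcomes, from 16 weeks before LMP2 to the end of pregnancy. STEP 3 already words the teratogenic-drug exclusion this way. Second- and third-trimester starters would then enter MCM_unexp, as Section 9.3.1 says. If never-users are in fact wanted as the MCM comparator, then objectives 1b and 2, the Abstract, Section 9.3.1 and Table 5 need changing instead. The preferred change is one clause in each of two steps and needs no extra data.
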